8.4 Withdrawal of individual subjects

Subjects can leave the study at any time for any reason if they wish to do so without any consequences. The investigator can decide to withdraw a subject from the study for urgent medical reasons.

8.4.1 Specific criteria for withdrawal (if applicable)

Not applicable.

8.5 Replacement of individual subjects after withdrawal

Patients will not be replaced after withdrawal.

8.6 Follow-up of subjects withdrawn from treatment

Regular follow up will be performed for all patients.

8.7 Premature termination of the study

In case of significantly increased incidence of serious side-effects in patients within the intervention group, the study will be ended. Otherwise inclusion will continue. Serious side effects might be cardiac arrhythmias or other exercise related problems during the VO₂ maximal intensity exercise tests.

9. SAFETY REPORTING

9.1 Temporary halt for reasons of subject safety

In accordance to section 10, subsection 4, of the WMO, the sponsor will suspend the study if there is sufficient ground that continuation of the study will jeopardize subject health or safety. The sponsor will notify the accredited METC without undue delay of a temporary halt including the reason for such an action. The study will be suspended pending a further positive decision by the accredited METC. The investigator will take care that all subjects are kept informed.

9.2 AEs, SAEs and SUSARs

9.2.1 Adverse events (AEs)

Adverse events are defined as any undesirable experience occurring to a subject during the study, whether or not considered related to trial procedure. All adverse events reported spontaneously by the subject or observed by the investigator or his staff will be recorded.

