5. TREATMENT OF SUBJECTS

5.1 Investigational product/treatment

1. Patient triage medical conditions

Patient triage will allow us to tailor perioperative management, which may lower the risk for postoperative complications 30% in 'the risky' group. An anaerobic threshold (AT) value of the VO₂max test of 10 ml/kg/min gives 0.88 specificity and 0.79 sensitivity with area under curve of 0,85 for risk of complications.⁵³ Also severe pulmonary and cardiac disease will often be detected and scaled upon severity with exercise testing.

Triage will also focus on anemia, to identify patients' cardiopulmonary comorbidity using VO₂ peak tests. Patients will be screened preoperatively (4 weeks before surgery) to capture insufficient hemoglobin levels (thresholds in Canada: >11.2 g/dl, Europe: >7mmol/l). In case of iron insufficiency, hemoglobin levels will be optimized using iron injections. In combination with training it may give substantial effect.

Triage described above will be applied to the intervention group as well as controls.

2. Prehabilitation intervention

The intervention described below will only be given to the intervention arm of this study. The only exception is the smoke-cessation program, which will be offered to all patients.

Exercise program

An exercise specialist (kinesiologist, sport physician) will assess patients' mobility and capacity to undertake exercise. All participants will undergo a cardiopulmonary exercise test (CPET) and the exercise intensity will be defined and personalized on the individual CPET values. Based on the evaluation, a personalized program from the standardized program will be coordinated, as defined in appendix II. Additional to the preoperative exercise program, patients will receive information regarding breathing techniques to prevent occurrence of pneumonia.

With the intervention we try to achieve a maximum training stimulus in combination with a recovery diet, in order to achieve these goals in 4 weeks.

The program exists of several components:

- Strength training and high intensity interval training: this will be done 3 times a week supervised in the hospital. The strength training consists of 2 series of 10 repetitions of 6 exercises targeting all major muscle groups. The high intensity interval training aimed at 90% of the VO₂-peak
- Homework endurance training (low to moderate intensity): 4 times a week done at home.

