All patients in the intervention group will be given instructions on relaxation and breathing techniques by a trained investigator. They will be given an instruction CD, which they can use for relaxation techniques at home. After the program, patients will be asked if their perceived usefulness of these techniques.

Also, as a form of psychological support, the intervention group will be contacted weekly by the investigator by phone. During these 5-15 minute phone calls, a researcher will shortly evaluate the following themes:

- General health perception of the patient: "how are you doing?"
- Evaluation of anxiety and use of anxiety reduction techniques.
- Evaluation of training: attendance, side effects/injuries, factors limiting attendance or completion of exercises.
- Evaluation of dietary intervention (protein supplement and advice): evaluate adherence and side effects.
- If relevant: smoking-cessation. Perception of usefulness of the program, smoking status (active smoker/stopped?), side effects.
- Any other questions the patient may have.

In order to enhance adherence to the prehabilitation program, all patients in the intervention group will receive an instructional brochure that includes information about all elements of the program.

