- o The last bout with 10 repetitions needs to be attainable. If this is not the case in the next session dosing will be 5-10% lower. If in the last bout it appears that exercises are too low (≥ 15 repetitions will be achieved), in the next sessions dosing will be 5-10% higher.

[figure not shown]
Homework/Counseling:

- The homework will be done at the days without supervised training, this will be a total of four days a week.
- Patients are instructed to aim at 60 minutes walking and/or cycling a day, but at least 30 minutes a day. If possible, patients can do more than 60 minutes of walking or cycling every day.
- Because of the low exercise capacity it is advised to walk/cycle 2-3 times a day for periods of 10-20 minutes.
- Also an electric bicycle, a stationary bicycle and/or a walking aid (walker) may be necessary.

Rest:

- Patients are instructed to take care of recovery and adequate rest and sleep.
- From 3 days before surgery no high intensive interval training and strength training are done. The patient will continue with the homework/counseling (walking/cycling every day) and the dietary supplements.

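### Before surgery, adverse events are recorded passively while only the prehabilitation arm has frequent staff contact and is asked about side effects, so pre-operative (mainly non-serious) event counts are not comparable between arms

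*Protocol*

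**What the plan says.** **Capture rule.** Protocol section 9.2.1 covers the whole study and both arms: "All adverse events reported spontaneously by the subject or observed by the investigator or his staff will be recorded". Events count whether or not they are thought to be related to trial procedures. No scheduled question about events, put alike to both arms, is stated.

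**Contact before surgery.** Under section 5.1, "The intervention described below will only be given to the intervention arm of this study", with smoking cessation the one exception. Of strength and interval training it says that "this will be done 3 times a week supervised in the hospital". Appendix II adds a short pause: "From 3 days before surgery no high intensive interval training and strength training are done". Section 5.1 also states that "the intervention group will be contacted weekly by the investigator by phone". The topics of the call include an open question on general health, "Evaluation of training: attendance, side effects/injuries, factors limiting attendance or completion of exercises", a similar check on unwanted effects of the nutritional component, and, where relevant, side effects of smoking cessation.

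**What both arms share.** Section 3 applies the Appendix I measurements to both arms. Before surgery these fall at weeks -4 and -1, and after surgery at weeks 4, 8 and 52. The smoking-cessation programme is offered to all patients.

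**Stopping rule.** Section 8.7 ends the study "In case of significantly increased incidence of serious side-effects in patients within the intervention group". The examples given there are arrhythmias and other exercise-related problems during the maximal exercise tests.

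**The concern.** When events are recorded only if volunteered or noticed, the number recorded depends on how often staff see the patient and whether they ask. Here contact and questioning differ by arm in weeks -4 to 0, the period in which training could cause harm.

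The clearest sign of an artefact is smoking cessation. Both arms are offered the same programme, but only one arm is asked weekly about its side effects. The same holds for the general-health question: symptoms of the cancer or an intercurrent illness are more likely to reach the event form in the prehabilitation arm although training has nothing to do with them.

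At stake is the reading of pre-operative safety. An excess in the prehabilitation arm could be harm or closer observation, and no later analysis can separate the two, because events never elicited from controls are lost. This is a data-collection rule, so a statistical analysis plan could not repair it.

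**Working it through.** **1. Scheduled contacts before surgery**

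Inputs: three sessions a week and weekly calls (section 5.1); no interval or strength training from 3 days before surgery (Appendix II); test visits at weeks -4 and -1 (Appendix I). I take the calls to run over the 4 weeks of prehabilitation.

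- Sessions: 3 × 4 = 12 at most. With the pause, 28 - 3 = 25 days and 3 × 25/7 = 10.7, so about 11.
- Calls: 1 × 4 = 4.
- Extra contacts in the prehabilitation arm: 11 + 4 = 15, up to 12 + 4 = 16.
- Scheduled test visits in both arms: 2. Patients are randomised during the baseline measurements (section 10.2), so only the week -1 visit falls clearly after allocation.
- Total: about 17-18 against 2. The 2 counts test visits only. Controls also have anaesthetic screening at week -1 and, if they smoke, cessation counselling.

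**2. Apparent rate ratio with no true difference**

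With equal true incidence, apparent ratio = capture in the prehabilitation arm / capture in controls. The protocol gives no capture fractions, so these are assumptions.

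| Events | Prehabilitation capture | Control capture | Apparent ratio |
|---|---|---|---|
| Non-serious | 95% | 70% | 0.95/0.70 = 1.36 |
| Non-serious | 95% | 50% | 0.95/0.50 = 1.90 |
| Serious | 100% | 90% | 1.00/0.90 = 1.11 |
| Serious | 100% | 100% | 1.00 |

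**3. Chance of a nominally significant excess**

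The protocol states no adverse-event rate or safety threshold to reproduce. Its arm size does reproduce: for a CCI difference of 0.30 × 10.4 = 3.12 with SD 14, two-sided alpha 0.05 and power 0.80, a t-test needs 318 per arm, and 318/0.90 = 353.3, rounded up to 354 (708 in total).

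With n = 354 per arm, true incidence p in both arms, full capture in the prehabilitation arm and relative capture r in controls, the recorded proportions are p and rp. For a two-sided 5% test,

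P(significant excess) = Φ{[(p - rp) - 1.96·SE0]/SE1},

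where SE0 = √[2·p̄(1 - p̄)/n], p̄ = (p + rp)/2, and SE1 = √{[p(1 - p) + rp(1 - rp)]/n}.

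| True incidence p (assumed) | r = 1 | r = 0.90 | r = 0.75 | r = 0.50 |
|---|---|---|---|---|
| 2% | 2.5% | 3.9% | 7.3% | 19.3% |
| 5% | 2.5% | 5.0% | 12.6% | 41.7% |
| 10% | 2.5% | 6.6% | 21.7% | 71.5% |
| 30% | 2.5% | 14.1% | 62.1% | 99.8% |

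Example: p = 2%, r = 0.50 gives SE0 = 0.00914, SE1 = 0.00913 and (0.010 - 0.0179)/0.00913 = -0.87, so 19.3%.

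Common events that depend on contact lie towards the lower right of the table. Rare serious events with near-complete capture lie at the upper left, close to 2.5%.

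**4. Section 8.7 against the schedule**

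The rule concerns serious side-effects. Section 9.2.2 defines a serious event mostly by outcomes such as death, threat to life or hospitalisation, which come to light without frequent contact. The criterion resting on investigator judgement of other important medical events depends more on contact. Section 8.7's own examples arise in exercise tests that both arms take at the same visits under staff observation, so for those the differential is absent.

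**The case against.** The strongest reply has four parts.

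- **The stopping rule is hardly touched.** A reader might infer that the prehabilitation arm's rate is higher by construction in the comparison that can end the study. The documents do not support this. Section 8.7 covers serious side-effects only, its examples occur in tests common to both arms, and the plausible ratio for serious events includes 1.0. It also names no comparator or test, so a between-arm comparison is implied rather than stated. This part of the reply stands.
- **Controls are not unobserved.** At week -1 they see several staff and complete quality-of-life, anxiety and depression questionnaires and the PG-SGA, which asks about recent nutrition-related symptoms. A complaint raised there could be recorded under section 9.2.1. This stands as a limit on the contact count. These instruments are not event enquiries, however, and both arms complete them, so they do not close the gap.
- **The size is assumed, and some excess would be real.** Both are true. A contact count does not yield a capture fraction, and an injury caused by training is an effect of the intervention. But the general-health and smoking-cessation questions also draw out events unrelated to training, in one arm only.
- **Unequal contact is inherent in supervised exercise, event rates are not an endpoint, and the DSMB can allow for closer observation.** The extra contact is unavoidable; the lack of a common question is not. The DSMB could weigh the source of an event only if the form recorded it.

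**Conclusion.** The point holds as a limited one. Under the protocol as written, recorded pre-operative adverse events, mainly non-serious ones, are expected to be inflated in the prehabilitation arm relative to controls. The direction follows from the capture rule and the contact schedule. The size cannot be derived from the protocol: a ratio of 1.4 to 1.9 for non-serious events rests on assumed capture of 95% against 50-70%, and about 1.0 to 1.1 for serious events on assumed control capture of 90-100%.

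The section 8.7 judgement may be affected slightly, through serious events that neither lead to admission nor occur in the shared tests. Section 9.2.1 applies throughout the study; the concern is confined to the pre-operative weeks because Appendix I gives both arms the same visits after surgery. The primary endpoints are not at issue. The change is worth making because it is cheap and the lost information cannot be recovered later.

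**What to change.** 1. In section 9.2.1, ask both arms the same short question about health events since the last assessment at the existing week -1, 4 and 8 visits.
2. Add a source flag to the event form: common question, training session, weekly call or hospital record.
3. Base between-arm adverse-event rates on the commonly ascertained events, and list events found only at sessions or calls separately for the prehabilitation arm.
4. Keep all serious events, including those seen in training sessions, in the section 8.7 review, with the source shown to the DSMB. Restricting that review to commonly ascertained events could remove a real training harm from it.

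Cost: one extra question at visits already planned and one extra form field. No added visits are needed.

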9.2.2 Serious adverse events (SAEs)

A serious adverse event is any untoward medical occurrence or effect that

- results in death;
- is life threatening (at the time of the event);
- requires hospitalization or prolongation of existing inpatients' hospitalization;
- results in persistent or significant disability or incapacity;
- is a congenital anomaly or birth defect; or
- any other important medical event that did not result in any of the outcomes listed above due to medical or surgical intervention but could have been based upon appropriate judgement by the investigator.

An elective hospital admission will not be considered as a serious adverse event.

Since the participants in the study are operated for colorectal cancer AEs and SAEs are to be expected in both study arms. The primary endpoint of the study is the complication ratio expressed as the Comprehensive Complication Index. All SAEs will be discussed with among the surgeons in each participating hospital.

All SAEs will be reported through the web portal *ToetsingOnline* to the accredited METC that approved the protocol, within 15 days after the sponsor has first knowledge of the serious adverse reactions.

SAEs that result in death or are life threatening should be reported expedited. The expedited reporting will occur not later than 7 days after the responsible investigator has first knowledge of the adverse reaction. This is for a preliminary report with another 8 days for completion of the report.

9.2.3 Suspected unexpected serious adverse reactions (SUSARs)

Not applicable.

9.3 Annual safety report

Not applicable.

9.4 Follow-up of adverse events

All AEs will be followed until they have abated, or until a stable situation has been reached. Depending on the event, follow up may require additional tests or medical procedures as indicated, and/or referral to the general physician or a medical specialist.

SAEs need to be reported until the end of the study, as defined in the protocol.

9.5 Data Safety Monitoring Board (DSMB) / Safety Committee

An independent Data Safety Monitoring Board (DSMB) will be asked to monitor the progress of the study and the safety of its participants. The DSMB will include: Dr. [name] MD PhD, surgeon, Jeroen Bosch Hospital, 's Hertogenbosch, Dr. [name], epidemiologist, Dr. [name], sports physician, Máxima Medical Center, Eindhoven –Veldhoven. The DSMB will meet as required to review any expected

adverse events and may ask to review outcomes or other data that may have an impact on the trial. **Every 10 SAEs will be reported to the DSMB by the sponsor.**

The advice of the DSMB will only be sent to the sponsor of the study. The sponsor will decide if the advice of the DSMB will be implemented. And will subsequently update the reviewing METC on this advice including a note to substantiate why (part of) the advice of the DSMB will not be followed).

STATISTICAL ANALYSIS

Data will be analyzed according to a detailed statistical analysis plan, which will be available before the final data freeze to allow for corrections based on data checks and database cleaning

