Sponsor	The sponsor is the party that commissions the organisation or performance of the research, for example a pharmaceutical company, academic hospital, scientific organisation or investigator. A party that provides funding for a study but does not commission it is not regarded as the sponsor, but referred to as a subsidising party.
SUSAR	Suspected Unexpected Serious Adverse Reaction
Wbp	Personal Data Protection Act (in Dutch: Wet Bescherming Persoonsgegevens)
WMO	Medical Research Involving Human Subjects Act (in Dutch: Wet Medisch-wetenschappelijk Onderzoek met Mensen)

SUMMARY

Rationale: Colorectal cancer (CRC) is the second most prevalent type of cancer in the World. The only curative treatment is surgical removal of the tumor. However, postoperative complications occur in up to 50% of patients and are associated with a higher mortality- and return of cancer rate and increased hospital costs. The number and severity of complications is closely related to preoperative functional capacity, nutritional state and smoking behavior. Traditional approaches have targeted the per- and postoperative period for rehabilitation and lifestyle changes. However, recent evidence shows that the preoperative period might be the optimal time frame for intervention.

Objective: This study will determine the effects of multimodal prehabilitation on functional capacity and postoperative complications in patients with colorectal cancer.

Study design: International multicenter, prospective, randomized controlled trial.

Study population: Adult patients undergoing elective surgery for colorectal cancer.

Intervention: Patients will be allocated to an intervention group, receiving 4 weeks prehabilitation (group 1, prehab) or to the control group receiving no prehabilitation (group 2, no- prehab). Both groups obtain 8 weeks rehabilitation postoperatively following ERAS guidelines, which is standard care.

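### A bare count of ten is the only stated trigger for sending SAEs to the DSMB, with no prompt route for fatal, life-threatening, preoperative or exercise-related events

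*Protocol*

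**What the plan says.** **DSMB (protocol 9.5).** The board monitors progress and participant safety. Its supply of SAEs is governed by one sentence: "Every 10 SAEs will be reported to the DSMB by the sponsor". Meetings have no calendar: "The DSMB will meet as required to review any expected" adverse events. The board also "may ask to review outcomes or other data that may have an impact on the trial". Its advice goes to the sponsor, who decides whether to follow it.

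**METC (protocol 9.2.2).** Every SAE is reported within 15 days of the sponsor learning of it. For fatal or life-threatening SAEs, "The expedited reporting will occur not later than 7 days after the responsible investigator has first knowledge of the adverse reaction". Surgeons at each hospital also discuss all SAEs.

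**What counts as an SAE (protocol 9.2.2).** An event qualifies if, among other criteria, it "requires hospitalization or prolongation of existing" inpatient stay. The section adds: "Since the participants in the study are operated for colorectal cancer AEs and SAEs are to be expected in both study arms".

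**Early termination (protocol 8.7).** The study ends if serious side effects are significantly more frequent in the intervention group. The examples are arrhythmias and other exercise-related problems during maximal exercise testing.

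**The concern.** The trigger counts SAEs whatever their cause, severity, arm or timing. A death or a serious arrhythmia before surgery adds one to the count, and nothing in 9.5 requires it to be sent until the count reaches ten. The METC has a 7- or 15-day clock for the same event; the board charged with participant safety has no clock.

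The content of the reports matters too. The rule in 8.7 is a comparison that singles out the intervention arm and names exercise-related events. Section 9.5 does not require a report of ten SAEs to show arm, or whether the event fell before or after surgery. As written, the DSMB need not receive what 8.7 would have someone judge.

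At stake is how quickly an independent board, whose members include a sports physician, learns of the kind of event that the protocol itself names as its main safety concern.

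**Working it through.** **Inputs from the protocol**
- 708 patients, 354 per arm (4.4); inclusion over about 2 years (section 3), taken as 104 weeks.
- Batch of ten SAEs (9.5).
- METC limits of 15 and 7 days (9.2.2).
- In the summary and introduction: "postoperative complications occur in up to 50% of patients". This is a ceiling for complications of any grade, not an SAE rate.

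**Assumption.** The protocol gives no SAE rate. Let r be the share of patients with one SAE each, with r from 15% to 50%. The top of the range treats every complication as an SAE.

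**Reproducing the plan's figure.** The batch of ten has no derivation to check. The sample size behind the accrual rate does: difference 0.30 × 10.4 = 3.12, SD 14, two-sided alpha 0.05 and power 0.80 give 317 per arm. Then 317/0.90 = 352.2, rounded up to 353 per arm, or 706 in total against the stated 708. I use 708.

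**Rates.** Accrual is 708/104 = 6.81 patients per week, so SAEs arrive at 6.81 × r per week.
- The event that opens a batch waits for nine more: 9/(6.81 × r) weeks.
- An event equally likely to hold any of the ten positions waits on average (0 + 1 + … + 9)/10 = 4.5 gaps: 4.5/(6.81 × r) weeks.

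| r | SAEs per week | Wait if it opens a batch (weeks) | Average wait (weeks) |
|---|---|---|---|
| 15% | 1.02 | 8.8 | 4.4 |
| 20% | 1.36 | 6.6 | 3.3 |
| 30% | 2.04 | 4.4 | 2.2 |
| 50% | 3.40 | 2.6 | 1.3 |

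**Against the METC clocks**
- 7 days: the shortest average wait, 1.3 weeks (about 9 days), is longer.
- 15 days (2.14 weeks): an event that opens a batch waits longer at every rate shown. The average wait is longer only when r is below 4.5/(6.81 × 2.14), about 31%.

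**What moves these figures**
- *Start-up.* Section 3 names two of the six centres to start in May 2017 and the rest during 2017. If early accrual were one third of the average (an assumption; no site volumes are given), the waits triple: 7.9 to 26.4 weeks for an event that opens a batch.
- *First weeks.* Appendix I puts the baseline exercise test at week −4 and surgery at week 0. In the first month there are almost no operations to generate SAEs, so an early exercise event waits whatever r is.
- *Repeat SAEs.* Two SAEs per affected patient would halve the waits, to 1.3 to 4.4 weeks for an opener and 0.7 to 2.2 weeks on average. The lowest of these falls inside 7 days.

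**The case against.** The strongest reply is that no SAE goes unseen. The METC receives each one, local surgeons discuss each one, and under 9.1 the sponsor must suspend the study if safety is in jeopardy. The DSMB can meet when needed and ask for data. It advises and the sponsor decides, so hearing after the METC is a difference between two channels rather than a contradiction. Section 11.2 classes the study as minimal risk, and batching is a legitimate choice.

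Most of this stands, and it keeps the point modest. It does not close the gap: the right to request data helps only a board that already knows of an event. The annual safety report (9.3) and SUSAR reporting (9.2.3), which might have supplied another route, are marked not applicable.

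A reader might be tempted by stronger readings that the text does not support:
- *That batches are pooled across arms.* Section 9.5 is silent on layout; it merely does not require a split.
- *That almost all SAEs will be surgical.* Surgical SAEs are expected in both arms, but no rate or share is given.
- *That an exercise event would be lost among the others.* In a list of ten it is still one in ten, and a sports physician is on the board.
- *That every event waits for nine others.* Only the one that opens a batch does; the tenth does not wait.
- *That the word expected steers the board away from exercise events.* The protocol foresees arrhythmias and exercise-test problems, so the word can include them; equally, it may be a slip for unexpected. This is a query about wording.

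**Conclusion.** The point holds in a limited form. The only stated trigger for sending SAEs to the DSMB is a count of ten, with no time limit, no exception for fatal, life-threatening, preoperative or exercise-related events, and no requirement to show arm or period. That sits poorly with the METC clocks in 9.2.2 and with the arm-specific rule in 8.7.

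The delay is about 2.6 to 8.8 weeks for an event that opens a batch and about 1.3 to 4.4 weeks on average. It rests on an assumed 15% to 50% of patients with one SAE each, arriving steadily at 6.81 patients per week. The direction is secure; the size is not, because the protocol gives no SAE rate. Participants are not left unprotected, since the METC and sponsor see each event. This is a cheap improvement to safety oversight.

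**What to change.** In 9.5, keep the batch of ten for all other SAEs, and copy the following to the DSMB on the same 7- or 15-day clock as the METC report:

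1. every SAE between the baseline exercise test and surgery;
2. every SAE that occurs during, or is judged related to, an exercise test or training session, at any time;
3. every fatal or life-threatening SAE.

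Item 2 should not be widened to any SAE after an exercise test. All patients have a baseline test, so that wording would capture every SAE and abolish the batch.

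Tabulate each batch by arm and by period (before or after surgery). State whether the adverse events that prompt a DSMB meeting are meant to be expected or unexpected ones. Reconcile 8.7, 9.2.2 and 9.5 so that the DSMB receives the information the termination rule depends on; no change to that rule is proposed here.

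The cost is a few sentences in 9.5, one more recipient for reports already written for the METC, and some additional DSMB notifications.
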